## **6.2. Preparation, Handling, Storage, and Accountability**

The excipients used in the nirmatrelvir tablets/ritonavir capsules are safe for administration to pediatric participants.

Study intervention will be self-administered by the pediatric participant or administered to the pediatric participant by the parent/caregiver.

1. The investigator or designee must confirm that appropriate conditions (eg, temperature) have been maintained during transit for all study interventions received and any discrepancies are reported and resolved before use of the study intervention.
2. Only participants enrolled in the study may receive study intervention and only authorized site staff may supply, prepare, and/or administer study intervention.
3. All study interventions must be stored in a secure, environmentally controlled, and monitored (manual or automated recording) area in accordance with the labeled storage conditions with access limited to the investigator and authorized site staff. At a minimum, daily minimum and maximum temperatures for all site storage locations must be documented and available upon request. Data for nonworking days must indicate the minimum and maximum temperatures since previously documented upon return to business.
4. Any excursions from the study intervention label storage conditions should be reported to Pfizer upon discovery along with actions taken. The site should actively pursue options for returning the study intervention to labeled storage conditions, as soon as possible. Once an excursion is identified, the study intervention must be quarantined and not used until Pfizer provides permission to use the study intervention. Specific details regarding the excursion definition and information to report for each excursion will be provided to the site in the IPM.
5. Any storage conditions stated in the SRSD will be superseded by the storage conditions stated on the label. Site staff will instruct participants on the proper storage requirements for take-home study intervention.
6. Study interventions should be stored in their original containers.
7. The investigator, institution, head of the medical institution (where applicable), or authorized site staff is responsible for study intervention accountability, reconciliation, and record maintenance (ie, receipt, reconciliation, and final disposition records), such as the IPAL or sponsor-approved equivalent. All study interventions will be accounted for using a study intervention accountability

form/record. All nirmatrelvir/ritonavir that is taken home by the participant, both used and unused, must be returned to the investigator by the participant. **Returned study intervention must not be redispensed to the participants.**

8. Further guidance and information for the final disposition of unused study interventions are provided in the IPM. All destruction must be adequately documented. If destruction is authorized to take place at the investigator site, the investigator must ensure that the materials are destroyed in compliance with applicable environmental regulations, institutional policy, and any special instructions provided by Pfizer.

Upon identification of a product complaint, notify the sponsor within 1 business day of discovery as described in the IPM.

### **6.2.1. Preparation and Dispensing**

A qualified staff member will dispense the nirmatrelvir/ritonavir using unique container numbers via an IRT system in the bottles and blister cards provided, in quantities appropriate according to the [SoA](#). A second staff member will verify the dispensing. The participant/caregiver should be instructed to maintain the product in the bottle and blister cards, as provided throughout the course of dosing and return the bottle and blister cards, as appropriate to the site at the next study visit.

The study intervention will be administered in a blinded fashion to the participants.

### **6.3. Assignment to Study Intervention**

Allocation of participants to treatment groups will proceed through the use of an IRT system. The site personnel (study coordinator or specified designee) will be required to enter or select information including but not limited to the user's ID and password, the protocol number, and the participant number. The site personnel will then be provided with a randomization number corresponding to the assigned treatment group, and DU or container number(s) when study intervention is being supplied via the IRT system. The IRT system will provide a confirmation report containing the participant number, randomization number, and DU or container number assigned. The confirmation report must be stored in the site's files.

For the main study population, randomization will be stratified by participants who are considered immunocompromised solely based on corticosteroids or TNF blocker use (yes/no). Enrollment of participants who are considered immunocompromised solely based on corticosteroids or TNF blocker use will be capped at approximately 25% for the main study population.

Randomization for the population with rebound will not be stratified by those who are considered immunocompromised solely based on corticosteroids or TNF blocker use. Enrollment of participants considered immunocompromised based solely on receiving corticosteroids or TNF blockers in the additional population with rebound will not be capped.

Study intervention will be dispensed at the study visits summarized in the [SoA](#).

The study-specific IRT reference manual and IPM will provide the contact information and further details on the use of the IRT system.

Returned study intervention must not be redispensed to the study participants.

The study-specific IRT reference manual and IPM will provide the contact information and further details on the use of the IRT system.

#### **6.4. Blinding**

This is a double-blind study.

##### **6.4.1. Blinding of Participants**

Participants and their caregivers will be blinded to their assigned study intervention.

##### **6.4.2. Blinding of Site Personnel**

Investigators and other site staff will be blinded to participants' assigned study intervention.

Participants will be assigned to receive study intervention according to the assigned treatment group from the randomization scheme. Investigators will remain blinded to each participant's assigned study intervention throughout the course of the study.

In the event of a Quality Assurance audit, the auditor(s) will be allowed access to unblinded study intervention records at the site(s) to verify that randomization/dispensing has been done accurately.

##### **6.4.3. Blinding of the Sponsor**

Sponsor staff will be blinded to participants' assigned study intervention.

Sponsor staff who are not directly involved with the conduct of this study will prepare analyses and documentation containing unblinded data while the study is ongoing to support interactions with the E-DMC.

The study will be unblinded after all participants complete the Day 44 visit (or ET prior to Day 44 visit) and analyses through Day 44, including the primary efficacy endpoint analyses, will be conducted.

Details of the unblinded sponsor staff supporting the E-DMC and the timing of unblinding will be outlined in the Unblinding Plan.

##### **6.4.4. Breaking the Blind**

The IRT will be programmed with blind-breaking instructions. In case of an emergency, the investigator has the sole responsibility for determining if unblinding of a participant's treatment assignment is warranted. Participant safety must always be the first consideration in making such a determination. If the investigator decides that unblinding is warranted, the investigator should make every effort to contact the study medical monitor prior to unblinding a participant's treatment assignment unless this could delay further management

of the participant. If a participant's treatment assignment is unblinded, the sponsor must be notified within 24 hours after breaking the blind. The date and reason that the blind was broken must be recorded in the source documentation and CRF.

The study specific IRT reference manual and IPM will provide the contact information and further details on the use of the IRT system.

## 6.5. Study Intervention Compliance

Participants will use a participant-completed electronic dosing diary to record the date and time of their study intervention dosing, and will be educated at the time of first dose.

Site personnel will review the participant-completed electronic dosing diary daily during the study intervention period, preferably after the participant has self-administered the morning dose of nirmatrelvir/ritonavir. If any noncompliance with dosing is suspected, site personnel will promptly contact the participant by phone, to remind them of the relevant study procedures and/or entering the information in the electronic diary as applicable.

When participants are dosed at the site, they will receive study intervention directly from the investigator or designee, under medical supervision. The date and time of each dose of study intervention administered in the clinic will be recorded by the participant in the diary. The dose of study intervention and study participant identification will be confirmed at the time of dosing by a member of the study site staff other than the person administering the study intervention.

When participants self-administer study intervention(s) at home, compliance with study intervention will be assessed at each visit. Compliance will be assessed by delegated study personnel upon return of study intervention through counting returned tablets/capsules and direct questioning, if applicable during the site visits and documented in the source documents.

A record of the number of nirmatrelvir tablets/ritonavir capsules dispensed to and taken by each participant must be maintained and reconciled with study intervention and compliance records.

The following noncompliance cases will be considered medication errors (see [Section 8.4.10](#)).

- Participants interrupting study intervention for 2 consecutive doses;
- Participants taking either nirmatrelvir or ritonavir alone for 2 consecutive doses;
- Participants who have an overall study intervention compliance <80% or >115%.

In addition to the above listed-medication errors, any deviation from protocol-specified dosing (eg, missed single dose or partial dose) should be recorded as a protocol deviation and

the investigator or designee is to counsel the participant/guardian and ensure steps are taken to improve compliance.

## 6.6. Dose Modification

The dose may need to be modified on Day 5 or Day 10, based on the eGFR or eCrCl result from the point-of-care device:

- Participants with a Day 5 or Day 10 eGFR  $<60$  mL/min/1.73 m^2 or eCrCl  $<60$  mL/min will receive a wallet consisting of 1 tablet of nirmatrelvir 150 mg and placebo for nirmatrelvir or 2 tablets of placebo for nirmatrelvir. The dose of ritonavir remains unchanged.
- Participants with a Day 5 or Day 10 eGFR  $>60$  mL/min/1.73 m^2 or eCrCl  $>60$  mL/min, will receive a wallet consisting of 2 tablets of nirmatrelvir 150 mg or 2 tablets of placebo for nirmatrelvir. The dose of ritonavir remains unchanged.

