**Table 1. Study Schedule of Assessment**

Visit Identifier' Abbreviations used in this table may be found in Section 10.11.	Screening	Baseline (Day 1)	Day 5	Day 10	Day 15	Day 21	Day 28	Day 35	Day 44	LTF/U		ET (pilot to Day 44)	Notes
										Week 12	Week 24		
Visit Window	Day -1 to Day 1	0 days	bl:1 day	bl:1 day	±2 days	±2 days	±2 days	±3 days	±3 days	±1 days	±7 days	±5 days	
 
Screening procedures may be done from Day -1 to Day 1, and may be completed on the same calendar day as Baseline/Day 1 procedures. If screening and baseline visits are conducted on the same calendar day, assessments and procedures that are listed to occur at both visits only need to be completed once.
 

Study intervention dispensation		X	X	X									
 
Study intervention will be dispensed on Day 1, Day 5, and Day 10 (see Section 6.1.1).
 
Should eGFR or eCrCl (based on the point-of-care creatinine) on Day 5 or Day 10 warrant a dose modification, replacement study intervention will be dispensed on Day 5 or Day 10. See Section 10.7.1 for age specific kidney function calculations.
 
See Section 6.6.
 

Study intervention administration		Day 1 through Day 15											
 
Baseline assessments should be performed before administration of the first study intervention, except for PK sampling.
 
The first dose of study intervention will be administered to all participants on Day 1 during the in person visit. All subsequent doses of study intervention (ie, 29) will be self-administered (or administered to the participant by a legal guardian or caregiver). If only 1 dose of study intervention is administered on Day 1, study intervention administration should end on Day 16.
 
See Section 6.1.1.
 

Study Intervention Accountability													
Retrieval of unused study intervention and empty study intervention containers			X	X	X							X	
 
If the Day 15 visit is conducted prior to last dose of study intervention, empty study intervention containers and unused study intervention should be returned at the Day 21 visit.
 
See Section 6.5.
 

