Results from the renal impairment study showed that the adjusted geometric mean (90% CI) test/reference ratios comparing moderate renal impairment (test) to normal renal function (reference) for nirmatrelvir  $AUC_{inf}$  and  $C_{max}$  was 187.40% (148.52%, 236.46) and 138.12% (113.18%, 168.55%), respectively. Due to the increase in exposures of nirmatrelvir in those with moderate renal impairment, and verified by modeling and simulation, the nirmatrelvir/ritonavir dose in patients with moderate renal impairment was reduced to 150 mg/100 mg.

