### **Medical Conditions:**

1. Current need for hospitalization or anticipated need for hospitalization within 24h after randomization in the clinical opinion of the site investigator.
2. Known medical history of active liver disease (other than nonalcoholic hepatic steatosis), including chronic or active hepatitis B or C infection, primary biliary cirrhosis, Child-Pugh Class C, or acute liver failure.
3. History of hypersensitivity or other contraindication to any of the components of the study interventions, as determined by the investigator.
4. Suspected or confirmed concurrent active systemic infection other than COVID-19 that may interfere with the evaluation of response to the study intervention.
5. Any comorbidity requiring hospitalization and/or surgery within 7 days prior to study entry, or that is considered life threatening within 30 days prior to study entry, as determined by the investigator.
6. Receiving dialysis or have known age-specific eGFR <30 mL/min/1.73 m^2 or eCrCl <30 mL/min at screening as measured by a serum creatinine point of care device ([Appendix 7, Section 10.7](#)).
7. Oxygen saturation of <92% on room air obtained at rest within 24h prior to randomization. (See [Appendix 9, Section 10.9.6](#)).
8. Other medical or psychiatric condition including recent (within the past year) or active suicidal ideation/behavior or laboratory abnormality that may increase the risk of study participation or, in the investigator's judgment, make the participant inappropriate for the study.

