Arm Title	Nirmatrelvir/ritonavir 5-day	Nirmatrelvir/ritonavir 10-day	Nirmatrelvir/ritonavir 15-day
Arm Type	Experimental, placebo	Experimental, placebo	Experimental
Arm Description	Participants will receive nirmatrelvir/ritonavir 300 mg/100 mg (or 150 mg/100 mg for participants with eGFR $\geq 30$ to $< 60$ mL/min/1.73 m  or eCrCl $\geq 30$ to $< 60$ mL/min) q12h from Day 1 through Day 5 followed by placebo for nirmatrelvir/placebo for ritonavir q12h for Day 6 through Day 15.	Participants will receive nirmatrelvir/ritonavir 300 mg/100 mg (or 150 mg/100 mg for participants with eGFR $\geq 30$ to $< 60$ mL/min/1.73 m  or eCrCl $\geq 30$ to $< 60$ mL/min) q12h from Day 1 through Day 10 followed by placebo for nirmatrelvir/placebo for ritonavir q12h for Day 11 through Day 15.	Participants will receive nirmatrelvir/ritonavir 300 mg/100 mg (or 150 mg/100 mg for participants with eGFR $\geq 30$ to $< 60$ mL/min/1.73 m  or eCrCl $\geq 30$ to $< 60$ mL/min) q12h from Day 1 through Day 15.
Associated Intervention Labels	Nirmatrelvir/ritonavir (5-day)	Nirmatrelvir/ritonavir (10-day)	Nirmatrelvir/ritonavir (15-day)

Nirmatrelvir/ritonavir may be shipped by courier to study participants if permitted by local regulations and in accordance with storage and transportation requirements for the nirmatrelvir/ritonavir. Pfizer does not permit the shipment of nirmatrelvir/ritonavir by mail. The tracking record of shipments, including temperature monitoring data, and the chain of custody of nirmatrelvir/ritonavir must be kept in the participant's source documents/medical records.

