### 6.1.1. Administration

The first dose of study intervention will be administered at the site.

Nirmatrelvir 150 mg tablets or placebo for nirmatrelvir will be administered with ritonavir 100 mg or placebo for ritonavir capsules for 15 days. Participants will be dispensed 1 blister wallet card of nirmatrelvir 150 mg tablets and 1 bottle of ritonavir capsules at the Day 1 site visit. Participants will be dispensed 1 blister wallet card of nirmatrelvir 150 mg or placebo for nirmatrelvir tablets and 1 bottle of ritonavir capsules or placebo for ritonavir at the subsequent Day 5 and Day 10 visits. Participants will be instructed to take:

- 2 tablets of nirmatrelvir 150 mg or placebo for nirmatrelvir q12h;
- 1 capsule of ritonavir 100 mg or placebo for ritonavir q12h.
  - Participants with moderate renal impairment (eGFR  $\geq 30$  to  $< 60$  mL/min/1.73 m^2 or eCrCl  $\geq 30$  to  $< 60$  mL/min at screening) will receive either 1 tablet of nirmatrelvir 150 mg and placebo for nirmatrelvir or 2 tablets of placebo for nirmatrelvir (Section 6.6). The dose for ritonavir remains unchanged (ie, participants will receive 1 capsule of ritonavir 100 mg or placebo for ritonavir q12h).

Participants should take the first dose of study intervention on Day 1, during the in-person visit; that is, participants should take 2 tablets of nirmatrelvir 150 mg and 1 capsule of ritonavir 100 mg at the same time and no more than 15 minutes apart. The study intervention should be taken every 12 hours ( $\pm 4$  hours), but no more than twice in a calendar day. Timing of the second dose of nirmatrelvir/ritonavir may be adjusted slightly to allow participants to select a convenient 12-hour dosing schedule as long as the second dose is taken at least 4 hours but no later than 16 hours after the first dose. Once the dosing schedule is adjusted, subsequent doses should be taken every 12 hours ( $\pm 4$  hours).

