## **7. DISCONTINUATION OF STUDY INTERVENTION AND PARTICIPANT DISCONTINUATION/WITHDRAWAL**

### **7.1. Discontinuation of Study Intervention**

It may be necessary for a participant to permanently discontinue study intervention. Reasons for permanent discontinuation of study intervention include the following:

- AE of Grade 3 severity or greater and considered by the investigator to be related to study intervention;
- SAE considered by the investigator to be related to study intervention;
- Requirement for prohibited concomitant medication;
- Participants who become pregnant during the course of the study;
- Study terminated by sponsor;
- Withdrawal by participant or legally authorized representative

- If post-screening eGFR <30 mL/min/1.73 m^2 or eCrCl is <30 mL/min the participant will be instructed to discontinue any remaining study intervention doses as soon as study staff become aware of the eGFR results.

In the event that a participant is hospitalized, study intervention may continue to be administered, as feasible, and based on medical judgment of the investigator.

Note that discontinuation of study intervention does not represent withdrawal from the study. If study intervention is permanently discontinued, the participant should remain in the study to be evaluated for all subsequent scheduled assessments. See the [SoA](#) for data to be collected at the time of discontinuation of study intervention and follow-up for any further evaluations that need to be completed.

In the event of discontinuation of study intervention, it must be documented on the appropriate CRF/in the medical records whether the participant is discontinuing further receipt of study intervention or also from study procedures, posttreatment study follow-up, and/or future collection of additional information.

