**Table 3. Protocol-Required Safety Laboratory Assessments**

Hematology	Chemistry	Other	Reflex Testing:
Hemoglobin	Urea	At screening only: FSH b	For suspected DILI: AST/ALT
Hematocrit	Creatinine		Total bilirubin, direct and indirect bilirubin
RBC count	eGFR or CrCl a ,	As per Schedule of	Total bile acids, GGT
Platelet count	Sodium	Activities:	Total protein, albumin
WBC count	Potassium	Pregnancy test	CK
Total neutrophils (Abs)	AST, ALT	(β-hCG) c	PT, INR
Eosinophils (Abs)	Total bilirubin	Thyroid function	Acetaminophen/paracetamol or
Monocytes (Abs)	Alkaline phosphatase	TSH	protein adduct levels
Basophils (Abs)	Albumin	T4 (free)	Hepatitis serology
Lymphocytes (Abs)	Total protein		
	Glucose (random)	Viral Serology	
	Calcium	SARS-CoV-2	
	Chloride		
	Total CO 2 (bicarbonate)		
	Renal Function for Eligibility and Determination of Dosing: eGFR or eCrCl will be assessed from creatinine value that will be obtained from a point-of-care device provided by the sponsor at screening (and also at baseline if screening and baseline visits are held on different days). An additional assessment may be performed on Day 5 or Day 10 at the investigator’s discretion		

- eGFR will be calculated using the method developed by the CKD-EPI for participants 18 years or older or eCrCl using the Cockcroft-Gault formula for participants 12 years to <18 years
- FSH testing is performed locally when needed to confirm postmenopausal status at screening.
- Local urine testing will be standard for the protocol unless serum testing is required by local regulation or IRB/EC. Serum or urine β-hCG for female participants of childbearing potential.

The investigator must review the laboratory report, document this review, and record any clinically relevant changes occurring during the study in the AE section of the CRF.

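### Protocol 6.6 dispenses the reduced-dose wallet at any Day 5/10 kidney-function value below 60, which conflicts below 30 with the mandatory stop in 7.1 (low severity)

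*Protocol*

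**What the plan says.** - **Protocol 6.6 (Dose Modification).** If the Day 5 or Day 10 point-of-care value is below 60 (eGFR or eCrCl), the participant "will receive a wallet consisting of 1 tablet of nirmatrelvir 150 mg and placebo for nirmatrelvir or 2 tablets of placebo for nirmatrelvir". The ritonavir dose does not change. A second bullet gives the full-dose wallet (or two placebo tablets) above 60. Neither bullet has a lower bound or refers to 7.1.
- **Protocol 7.1 (Discontinuation of Study Intervention).** A post-screening eGFR or eCrCl below 30 is listed among the reasons for permanent discontinuation: "the participant will be instructed to discontinue any remaining study intervention doses as soon as study staff become aware" of the result.
- **Protocol 6.1, arm descriptions (also in the Synopsis).** The 150 mg/100 mg dose applies at 30 or above and below 60.
- **Protocol 6.1.1.** The same wallet is described for moderate impairment at screening, with the same 30 to <60 range and a pointer to 6.6.
- **Protocol 4.3.** The justification covers moderate impairment only: "the nirmatrelvir/ritonavir dose in patients with moderate renal impairment was reduced to 150 mg/100 mg".
- **Protocol 5.2, Exclusion Criterion 6.** "Receiving dialysis or have known age-specific eGFR <30", or eCrCl below 30, at screening.
- **Schedule of Activities, dispensing note.** Should the Day 5 or Day 10 result "warrant a dose modification, replacement study intervention will be dispensed on Day 5 or Day 10". The note cites 6.1.1, 10.7.1 (for the kidney-function formulas) and 6.6. It does not cite 7.1.
- **Appendix 2, Table 3.** "An additional assessment may be performed on Day 5 or Day 10 at the" investigator's discretion.

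**The concern.** Sections 6.6 and 7.1 act on the same kind of result, a post-screening kidney-function value, and below 30 they ask for opposite things. One hands the participant more tablets and continues ritonavir; the other ends treatment. The reduced dose has a floor of 30 in the arm descriptions and in 6.1.1, so its absence from 6.6 looks like an oversight rather than a decision.

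What is at stake is a dispensing step at a visit. The protocol excludes people below 30 at entry and defines no regimen for them. A staff member who starts from the Schedule of Activities is sent to 6.6 and finds an instruction to dispense, with nothing there to point to the stop rule. Because the study is blinded, that person cannot tell whether the wallet holds active drug.

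**Working it through.** The documents give no figure to reproduce here. The check compares the rules as written. Let x be the Day 5 or Day 10 eGFR (mL/min/1.73 m²) or eCrCl (mL/min).

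**1. The rules as ranges**

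| x | Section 6.6 | Section 7.1 | Arm descriptions (6.1) |
|---|---|---|---|
| below 30 | reduced wallet, ritonavir unchanged | stop all remaining doses | outside the reduced-dose range; excluded at entry |
| 30 to <60 | reduced wallet | no action | reduced dose |
| above 60 | full wallet | no action | full dose |

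**2. Where they collide**

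- Overlap of the 6.6 reduced-wallet rule with the 7.1 stop: {x < 60} ∩ {x < 30} = {x < 30}.
- Part of the 6.6 rule outside the arm-description range: {x < 60} minus {30 ≤ x < 60} = {x < 30}.

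The two comparisons pick out the same region, so the whole discrepancy is the missing floor of 30. For example, x = 25 on Day 5 meets 25 < 60 (dispense) and 25 < 30 (stop).

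**3. What supports dosing below 30**

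Section 4.3 reports a nirmatrelvir AUCinf ratio of 187.40% (90% CI 148.52% to 236.46%) for moderate impairment against normal function, and bases the 150 mg dose on it. It gives no ratio for values below 30. The unbounded 6.6 rule therefore has no stated basis there.

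**4. How far it could reach**

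- Entry requires a value of at least 30, so only participants whose function falls during treatment can be affected.
- The Day 5 and Day 10 tests are optional, so some of those falls may not be measured.
- The supply handed out at each visit depends on the arm (Section 6.1):

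| Arm | Day 5 visit supply | Day 10 visit supply |
|---|---|---|
| 5-day | placebo | placebo |
| 10-day | active | placebo |
| 15-day | active | active |

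That is 3 arms × 2 visits = 6 supplies, of which 3 are active and 3 placebo. With 1:1:1 allocation, and assuming that a fall below 30 is equally likely in every arm, a wallet wrongly dispensed would be active with probability 2/3 at Day 5 and 1/3 at Day 10. The documents give no rate of falling below 30, so no count of participants follows.

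**5. After the correction**

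With bands <30 (stop), ≥30 to <60 (reduced) and ≥60 (full), every value falls in exactly one band and the overlap at x < 30 is empty.

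**The case against.** The strongest reply is that the two sections already fit together. Section 6.6 is about modifying a dose and opens in permissive terms; someone permanently discontinued has no dose left to modify. Section 6.6 makes no exception for the other 7.1 reasons either, such as pregnancy or a related Grade 3 event, and nobody would read it as ordering supply for those participants. The Schedule of Activities note is also conditional on a modification being warranted.

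Much of this stands. It is how a careful reader would reconcile the sections, and it keeps the severity low. It does not remove the conflict. The other stop reasons are not triggered by the creatinine result, whereas here both rules use it. Once a value below 30 is in hand, the 6.6 bullet is a firm instruction. Section 6.6 is also where the Schedule of Activities note sends the reader to learn when a modification is warranted, and its threshold is simply below 60.

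Three stronger readings are tempting, and the documents do not support them.

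- *The protocol lacks a stop rule below 30.* It has one, in 7.1, and it is explicit.
- *A value of exactly 60 is a second proven gap, because 6.6 as printed covers only below and above 60 while the arm descriptions would give full dose.* The dosage row in 6.1 and the text of 6.1.1 tie the reduced dose to the screening value, so the arm descriptions do not settle a Day 5 or Day 10 retest. The printed sign may also be a lost ≥: the Schedule of Activities gives >18 years for self-reported height where Section 8.3.1 gives ≥18.
- *Participants would come to measurable harm.* Without an exposure ratio or an event rate below 30, no risk can be estimated.

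**Conclusion.** Section 6.6 is wrong as written. It lacks the floor of 30 and, below that value, contradicts 7.1 and departs from the range in the arm descriptions and 6.1.1. Section 7.1 should prevail, so this is a correction to 6.6 and not a gap in the stop rule.

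Severity is low. Few participants can be affected, because the test is optional, entry excludes values below 30, and half of the arm-by-visit supplies are placebo. The primary estimand disregards study treatment discontinuation, so neither the endpoint nor its analysis changes.

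The conclusion rests on the printed text of 6.6 and 7.1 and does not depend on whether the full-dose bullet originally read > or ≥. Whether the dispensing system already blocks supply below 30 cannot be seen from these documents. If it does, the practical risk is smaller, but the text still needs correcting.

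**What to change.** In Protocol 6.6, state three bands for eGFR (mL/min/1.73 m²) or eCrCl (mL/min):

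- ≥30 to <60: reduced-dose wallet or placebo, ritonavir unchanged.
- ≥60: full-dose wallet or placebo, ritonavir unchanged (only if the source does not already read ≥60).
- <30: discontinue per Section 7.1; dispense no further study intervention.

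Add a reference to Section 7.1 to the dispensing note in the Schedule of Activities.

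The cost is a few lines of text in two places and no change to the analysis or sample size. Amendment 1 classed its edit of the kidney-function units in 6.6 and 7.1 as nonsubstantial. The sponsor would need to decide whether this wording change falls in the same class.
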